## Exclusion Criteria:

We excluded penetrating abdominal injury to focus on blunt abdominal injury in isolation. We excluded patients with known hypersensitivity reaction so that we could avoid SAE.

We excluded pregnant patients and prisoners as vulnerable populations.

We excluded patients without sufficient access because we would not be able to insert contrast.

## Subject recruitment plan:

Initial contact will be made by the study staff (clinical research coordinator, ASSET team, PI, co-investigator) upon presentation of potential subjects (i.e. subjects meeting the inclusion criteria) in the emergency room/hospital. Study staff will obtain written informed consent.

# Screening for eligibility:

In order to effectively screen potential patients for the study, the study personnel will ID subjects in the ED as appropriate through conferring with medical records, trauma logs, triage notes, radio reports of trauma alerts, and on-duty doctor and nurses to identify potential subjects. Many of the inclusion/exclusion criteria can be evaluated by a review of the potential subject's medical records such as: mechanism of injury, time of injury, presence or absence of concurrent penetrating trauma. All female patients of childbearing age will be offered a serum or urine pregnancy test (standard of care for evaluation of female trauma patient with suspected intra-abdominal injury). A patient may exercise their autonomy and waive pregnancy testing (due to reasons such as prior hysterectomy, tubal ligation) but are still eligible for the study as long as they are informed that Lumason is a Category B medication which means that animal studies have failed to demonstrate a risk to the fetus and there are no adequate and well-controlled studies in pregnant women. The patient's refusal of pregnancy test will be documented in the medical record. No identifiable data will be collected from subjects during screening.

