# 6. Study Design and Methods:

This single center prospective study will enroll 267 adult patients with hemodynamically stable blunt abdominal trauma who present to a Level 1 ACS verified Trauma Center.

Inclusion Criteria: Age 18 and older Clinical suspicion of intra-abdominal injury Presentation within 24 hours of injury Planned CT of the abdomen/pelvis within 24 hours Ability of patient to provide informed consent

Exclusion Criteria: Co-existing penetrating abdominal injury Known hypersensitivity reaction to contrast agent Pregnant patients Prisoners No appropriate IV Line able to be inserted Hemodynamic instability at time of enrollment (sustained systolic blood pressure < 90 mm Hg or sustained HR >120 despite initial resuscitation) Study Interventions/Procedures:

1) Baseline Grayscale US Exam

2) Contrast Enhanced US exam with IV administration of LUMASON

3) Chart Review for abstraction of clinical and demographic data

Risks/discomforts:

Risks from ultrasound use are minimal – this modality does not use ionizing radiation. Most commonly the patient may complain of coldness of gel or minor discomfort from pressure of the ultrasound probe.

The less common risks and discomforts expected in this study are (in 0.02% of patients):

Headache, nausea, dizziness, flushing, back pain, kidney pain, chest pain, shortness of breath, hypertension, mild allergic reactions

Rare but possible risks include: hypersensitivity to contrast resulting in low blood pressure (0.007% of patients).

Potential benefits include: identification of injuries with BEFAST not seen with conventional FAST

Ultrasound studies will be performed by a team of ultrasound faculty who have attended a didactic session on the BEFAST exam and grading of solid organ injury by AAST criteria. They will be evaluated with a post-test to check for comprehension.

After consent, a baseline FAST exam will be performed and documented. This FAST will be distinct from the initial ATLS resuscitation FAST in order to avoid any interference in the trauma evaluation. A 20g or larger intravenous line if not already placed, will be established according to standard practice for trauma patients. The investigator will use a phased array or curvilinear transducer to record video of their baseline FAST exam. The investigator will also note start/stop time of the FAST exam.

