Using the same machine, a BEFAST exam will be performed using a low mechanical index setting in contrast-specific imaging mode. Lumason will be injected into the patient's IV for the CEUS exam by either a nurse research coordinator or one of the clinical staff. The contrast will be injected using the straight port of a 3-way stopcock and flushed through the side port. To eliminate shear of microbubbles, contrast will not be injected through a clave connector. The contrast will be injected once for the right side of the body, and once for the left side of the body looking for disruptions in the normal enhancement pattern and evidence of active bleeding. If an antecubital line is placed, 2.4 mL contrast will be given over slow IV push (2-3 seconds) and flushed with 5 ml saline; if only a peripheral hand IV is established, the investigator may use a 10 ml saline flush.

To examine the right side of the body: the right kidney and liver will be imaged. The investigator will examine the RUQ for evidence of solid organ injury, free fluid, or active extravasation by examining the kidney in short and long views and the liver in coronal, anterior, and subcostal views.

The examiner will screen the liver during approximately the first 10-20 seconds after IV contrast administration to see hypoperfusion in the arterial phase or extravasation before scanning through all organs in the venous phase (kidney, then back to liver). The exam will be timed from start of saline flush after contrast and video clips will be saved (stored using patient study number).

To examine the left side of the body: the pancreas will be imaged first, followed by the kidney and the spleen. The investigator will note evidence of solid organ injury, free fluid, or active extravasation in the LUQ. The pancreas, kidney, and spleen will be visualized in short and long. The exam will be timed from start of saline flush after contrast and video clips will be saved. If adrenal glands are visualized on either side these may be recorded as well.

In general, the investigator will scan one side of body at time but may cross to the other side if imaging on one side is complete. Investigators will be allowed to re-dose contrast on either or both sides if the first examination is not clear or if there is inadequate time to complete the exam. Either right side or left side may be examined first.

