#### 10. Informed Consent Process

A research team member will consent the patient at Grady Memorial Hospital.

We are requesting a partial HIPAA waiver to look at identifiable patient information prior to consent as part of the screening process in order to see if a patient meets inclusion/exclusion criteria. Elements of interest include: name, medical record number, age, mechanism of injury, timing of injury, pregnancy status, institutionalization, vital signs, allergies.

We are not studying children, prisoners, pregnant women/fetuses, or patients with cognitive impairment. Students and employees are not targeted groups for enrollment.

We will ensure comprehension of the informed consent information by allowing the patient ample time to ask questions and have the patient express understanding of the study. The study team will explain the purpose, risks, and potential benefits of the study and patient will be given the option of continuing participation or stopping.

Study consent discussion will take place in Grady Memorial Hospital. Study staff (research coordinator, ASSET team, PI, or co-I) will conduct the discussion and obtain consent. We are not requesting a waiver of signed documentation of informed consent.

In the event that the patient is cognitively capable of consent for the study but has a physical impairment (such as a broken arm) that prevents them from signing the consent document, the research team will obtain a signature from a witness to the consent process who is not a member of the research team. The witness will sign the consent paperwork (their signature, time, and date), leaving the patient fields blank. An informed consent process note will also be filed to document the circumstances, who served as a witness, and the relationship of the witness to the patient (e.g. related or unrelated to subject).

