# Monitoring the Progress and Safety of the Trial

During the screening process, patients will be excluded if they belong to vulnerable populations such as pediatric, pregnant, or imprisoned patients or if they have a known hypersensitivity to ultrasound contrast agent.

Measures to protect participants against risk include use of a physician or certified health care professional (nurse practitioner, physician assistant or registered nurse) to administer contrast. Confidentiality of participants will be protected by keeping data and US images password protected. The study will utilize a code number as the only identifier for each subject and the master list will be kept under lock and key with access limited to the PI and study coordinator.

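### The pregnancy exclusion cannot be verified in patients who waive the pregnancy test, because the waiver is open-ended and no other check is specified

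*Combined protocol and SAP*

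**What the plan says.** The exclusion lists in section 6 (Study Design and Methods) and section 9 (Participant Selection) both name pregnancy with no qualifier: "Pregnant patients Prisoners No appropriate IV Line able to be inserted". The justification under Exclusion Criteria gives the reason: "We excluded pregnant patients and prisoners as vulnerable populations". Section 10 (Informed Consent Process) repeats the position: "We are not studying children, prisoners, pregnant women/fetuses, or patients with cognitive impairment". Section 14, under Monitoring the Progress and Safety of the Trial, describes what happens during screening: "patients will be excluded if they belong to vulnerable populations such as pediatric, pregnant, or imprisoned patients".

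The procedure itself is under Screening for eligibility. It begins with an offer: "All female patients of childbearing age will be offered a serum or urine pregnancy test". It describes that test as standard of care for these trauma patients. It then allows refusal: "A patient may exercise their autonomy and waive pregnancy testing (due to reasons such as prior hysterectomy, tubal ligation) but are still eligible". The condition follows at once: she is "still eligible for the study as long as they are informed that Lumason is a Category B medication", with an explanation of what the category means and that adequate studies in pregnant women are lacking. The refusal goes into the medical record.

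Section 10 also lists pregnancy status among the items that may be reviewed before consent.

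**The concern.** Five places in the protocol treat pregnancy as a bar to entry, and one of them offers this as a safeguard. The only section that says how pregnancy is established makes the test optional and keeps the patient eligible without it. What replaces the test is information given to the patient. Information about fetal risk matters only to someone who might be pregnant, so the screening text appears to allow for possible pregnancy among those who waive. Informing a patient is not the same as excluding her.

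At stake is participant protection. An unrecognised pregnant patient could pass screening as written. The exposure would come from the study: the contrast examination is a listed study procedure, and section 4 says that use of the agent in trauma is off-label. The plan for each participant is: "The contrast will be injected once for the right side of the body, and once for the left side of the body". That is two injections, and section 6 allows redosing. An IRB relying on sections 10 and 14 would expect an assurance that the screening section does not provide.

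**Working it through.** No arithmetic applies, and the plan states no figure to reproduce. The check is to follow each kind of patient of childbearing age through the text.

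1. **She accepts the test and it is positive.** She meets the exclusion in sections 6 and 9. The exclusion operates.
2. **She is already known to be pregnant from her records or history.** Section 10 allows pregnancy status to be reviewed before consent. The exclusion operates.
3. **She accepts the test and it is negative.** She is eligible, and her status has been checked.
4. **She waives the test for a reason of the kind given as an example.** Hysterectomy and tubal ligation describe patients in whom pregnancy is impossible or unlikely. She is eligible, and little is at stake.
5. **She waives the test for some other reason, and no pregnancy is known.** The screening text introduces its two reasons as examples and rests the waiver on patient autonomy, so it does not confine the waiver to case 4. She is eligible once informed, with the refusal recorded. Nothing else is required to establish her status.

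The gap is case 5. Three features of the text might have closed it:

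- **Record review.** This finds a pregnancy that someone has already recorded. It cannot find one that nobody has recognised or tested for.
- **Disclosure.** This informs the patient's choice. It does not establish whether the exclusion applies.
- **Documentation of refusal.** This records that status was not tested. It does not resolve the status.

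None of the three verifies the criterion in case 5. Set beside section 14, the result is that exclusion at screening is assured in cases 1 and 2 but not in case 5.

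The number of patients in case 5 cannot be derived. The documents give no share of women of childbearing age, no waiver rate and no pregnancy rate. A count built on assumed shares would in any event count untested patients, including those in case 4, and not pregnancies.

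**The case against.** The strongest reply is that nothing here is contradictory. The criterion excludes pregnant patients, not patients of unknown status. Neither section 10 nor section 14 requires a negative test. The screening section is simply how the criterion is ascertained: the test is offered to all women of childbearing age, it is standard of care in this setting, records are reviewed, and a patient who declines is informed and her refusal documented. The protocol sets all this out openly, and the reasons it mentions concern patients who are very unlikely to be pregnant.

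Much of this stands. A reader might infer that the exclusion is unenforceable altogether, or that the protocol permits pregnant patients to be enrolled. The documents support neither reading: the exclusion still catches positive tests and known pregnancies, and the waiver concerns testing, not a pregnancy that has been established. A reader might also infer that sections 10 and 14 forbid enrolling an untested patient. They do not say so. Nor is this a matter of sites following different rules, since the study is single-center. The protocol does not conceal the waiver from the IRB.

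What the reply does not answer is case 5. If unknown status is acceptable, the exclusion in practice covers recognised pregnancy only. The exclusion lists, the justification, and sections 10 and 14 do not say that. The standard-of-care remark does not help, because it describes the very test that may be waived.

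**Conclusion.** The concern holds in a limited form. In patients who waive testing and whose pregnancy is not otherwise known, the exclusion cannot be verified, because the waiver reasons are open-ended and no alternative check is specified. The protection stated in section 14 is therefore not assured by the screening procedure.

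This rests on reading the two waiver reasons as examples, which is how they are worded, and on the absence of any further check in the text available. Its size cannot be stated from the documents. The consequence is for participant protection and for the accuracy of what the protocol states. Sample size, power and the primary analysis are not affected. It should be corrected before enrolment relies on the present wording.

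**What to change.** Reconcile the waiver under Screening for eligibility with the exclusion lists in sections 6 and 9, the justification under Exclusion Criteria, the population statement in section 10 and the protection described in section 14, so that the procedure and the stated exclusion agree. Whether the procedure is brought into line with the stated exclusion, or the exclusion and protection are restated to match the procedure, is for the sponsor and the IRB to decide.

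The cost is a short amendment. In the first direction, a few patients who decline testing may be lost to enrolment. In the second, the protection is described as narrower than it now appears. No analysis or sample-size text needs to change.

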#### Procedures when a subject withdraws from a study:

In the case of withdrawal from study, videos saved up to the point of withdrawal may be kept as outlined in the study consent form. Once linkages are destroyed it will not be possible to identify an individual's video clips for destruction.

#### 10. Informed Consent Process

A research team member will consent the patient at Grady Memorial Hospital.

We are requesting a partial HIPAA waiver to look at identifiable patient information prior to consent as part of the screening process in order to see if a patient meets inclusion/exclusion criteria. Elements of interest include: name, medical record number, age, mechanism of injury, timing of injury, pregnancy status, institutionalization, vital signs, allergies.

We are not studying children, prisoners, pregnant women/fetuses, or patients with cognitive impairment. Students and employees are not targeted groups for enrollment.

We will ensure comprehension of the informed consent information by allowing the patient ample time to ask questions and have the patient express understanding of the study. The study team will explain the purpose, risks, and potential benefits of the study and patient will be given the option of continuing participation or stopping.

Study consent discussion will take place in Grady Memorial Hospital. Study staff (research coordinator, ASSET team, PI, or co-I) will conduct the discussion and obtain consent. We are not requesting a waiver of signed documentation of informed consent.

In the event that the patient is cognitively capable of consent for the study but has a physical impairment (such as a broken arm) that prevents them from signing the consent document, the research team will obtain a signature from a witness to the consent process who is not a member of the research team. The witness will sign the consent paperwork (their signature, time, and date), leaving the patient fields blank. An informed consent process note will also be filed to document the circumstances, who served as a witness, and the relationship of the witness to the patient (e.g. related or unrelated to subject).

# 11. Incidental Findings

The research team will relay any findings related to injury to solid organs and hemoperitoneum to the primary treatment team for further management. The FAST and BEFAST exams are screening exams only and not comprehensive abdominal exams; additional findings are not anticipated. If additional incidental findings are noted they will be relayed to primary treatment team for appropriate triage, referral to clinical specialists, and patient education as needed if the finding is clinically significant. All study patients will also obtain confirmatory imaging with CT study.

12. Compensation for time and effort: \$25 single payment as reimbursement for parking expenses, time, effort.

13. Statistical Analysis:

**Objective 1**: To determine if contrast-enhanced, i.e. bubble-enhanced FAST (BEFAST) outperforms non-enhanced FAST in the evaluation of solid organ injury in hemodynamically stable blunt abdominal trauma patients when performed by frontline providers using CT as gold-standard.

Descriptive Statistics. The primary results will be described using sensitivities and specificities with 95% confidence intervals. Categorical variables will be described using frequencies and percentages. Continuous variables will be described using means and/or medians as appropriate.

Primary Analyses. Agreement with the CT results will be examined using a mixedeffects/multi-level logistic regression in order to account for clustered measurements. Results from this regression will also be adjusted for the following covariates: demographics (e.g. age, sex, race), BMI, sonographer experience, contrast redosing, the presence of outward signs of injury. In the event that the logistic regression fails to estimate properly or provides poor fit to the data and/or to show consistent results across methods, alternative methods will be explored: (1) P-values and confidence intervals will be computed using a bias-corrected and accelerated bootstrapping procedure ( $\geq$ 5,000 resamples); (2) Sensitivities and specificities for BEFAST and FAST will be compared using McNemar's test.

Sample Size Calculations. Two primary issues were taken into consideration when calculating the required sample size: 1) statistical power, and 2) the expected rate of positive outcomes.

1) Power calculations were based on previous studies examining the sensitivity and specificity on standard and contrast-enhanced ultrasound. The results from these studies were meta-analyzed (fixed-effects, inverse-variance method) and indicated that (1) the sensitivity for CEUS (lower limit = 0.87) is greater than the sensitivity for standard ultrasound (upper limit = 0.68); and (2) the specificity for CEUS (0.98) is similar to the specificity for standard ultrasound (0.95). This analysis aimed to ensure that the present study has sufficient power to show improved sensitivity when using CEUS. Note that, because this sample size calculation uses the lower limit of the CEUS estimate and the upper limit of the standard ultrasound estimate, actual power will likely be greater. Given the small meta-analytic difference in specificities between methods, it is unlikely that differences in specificity will be detected. These values were used to estimate the sample size required to achieve 80% power using Monte Carlo simulations (10,000 samples) implemented in R v3.4.1. This analysis determined that the sample size would need to be at least 187.

2) Using the rule of thumb 10 positive results for each predictor, we aimed to ensure that there will be a sufficient number of positive results for a model with two predictors (i.e. at least 20 positives. Thus, the current study will aim for a sample size of at least 187; however, data collection will not end until at least 20 CT+ patients are enrolled. Importantly, this stopping rule is entirely a priori and ceasing data collection will not be dependent on any statistical analyses, significance tests, or interim analyses. No analyses will be conducted until after this stopping rule is reached.

Missing Data. In the event of substantial missing data, data will be imputed using a multiple imputation procedure. The type of procedure and the number of imputed data sets will be determined by the amount of missing data and the pattern of missingness. As a sensitivity analysis, we will 1) assume the worst and assign a "does not agree" outcome for that patient and 2) assume the best and assign an "agrees" outcome for that patient. These analyses will describe the boundary conditions for the models described above.

**Objective 2**: To determine whether emergency physicians can incorporate BEFAST evaluation at the point-of-care in a trauma evaluation of a hemodynamically stable adult blunt abdominal trauma patient.

An exam is complete if the patient tolerates the exam (no severe adverse reaction to contrast, patient allows the provider to complete the scan) and if it results in images of adequate quality to answer the focused clinical question.

Completion rates will be described as percentages with 95% confidence intervals. Assuming maximal variance for a binomial variable ( $\pi = 0.5$ ), a sample size of 187-267 (approximate) will result in 95% CIs that are no wider than  $\pm$  7.2% to 6.0%. FAST and BEFAST completion rates will be compared using either the multilevel/mixed effects logistic regression described above or McNemar's test.

**Objective 3**: To determine the interrater reliability between bedside emergency physicians and radiologists for identifying solid organ injury with BEFAST.

Inter-rater Reliability for the presence/absence of an injury will be evaluated using Cohen's or Fleiss' kappa as appropriate. The reliability of AAST scores will be evaluated using a weighted kappa statistic.

Assuming a minimal sample size of 187, the current study will have sufficient power ( $\geq$  80%) to detect reliability coefficients exceeding 0.23. For clinically relevant ratings, such as this, reliability is generally required to be high. Guidelines vary and are generally arbitrary; however, 0.8 and 0.9 are often used as cutoffs for "high" agreement, whereas a value such as 0.23 would be considered unacceptable. Thus, the current study is sufficiently powered to detect clinically acceptable levels of agreement.

14. Data and Safety Monitoring and Reporting:

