The investigator will note the presence or absence of injury to the liver, kidney, spleen, or pancreas, as well as the presence or absence of free fluid or active extravasation. If an injury to a solid organ is detected, the investigator will grade injury per American Association for the Surgery of Trauma (AAST) criteria. There will be an attestation noting whether there was unintended disclosure of either the primary team's FAST exam or CT imaging read prior to bedside interpretation of the BEFAST study. The investigator will note whether there were physical exam signs suggestive of injury that may have biased their interpretation. The investigator will note start/stop time of BEFAST exam. Exams will be saved to QPATH and to the US machine; the data will also be archived on an encrypted USB. QPATH will be password protected, and the USB will be kept in a locked file in a locked office. The US machine will be kept in a locked file in a locked office.

A study is complete if the patient tolerates the study (no severe adverse event to contrast, patient allows the provider to complete the scan) and if it results in images of adequate quality to answer the focused clinical question.

A serious adverse event (SAE) is defined by the FDA as any adverse drug event (experience) occurring at any dose that in the opinion of either the investigator or sponsor results in any of the following outcomes: 1) death 2) life-threatening adverse drug experience 3) inpatient hospitalization or prolongation of existing hospitalization (for > 24 hours) 4) persistent or significant incapacity or substantial disruption of the ability to conduct normal life functions 5) congenital anomaly/birth defect 6) important medical event (IME) that may not result in death, be life threatening, or require hospitalization may be considered a serious adverse drug experience when, based upon medical judgment, it may jeopardize the patient or subject and may require medical or surgical intervention to prevent one of the outcomes listed in this definition.

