For the FAST exam, the focused clinical question is whether there is free fluid in the abdomen or fluid in the pericardium. The following views should be obtained to meet minimum requirements: RUQ, LUQ, suprapubic, and subxiphoid views with adequate visualization of Morison's pouch, inferior pole of right kidney/liver tip, area under the diaphragm on the LUQ side, pelvic views in transverse and sagittal. If an adequate subxiphoid view is not possible, a parasternal long view may be substituted. For the BEFAST exam the focused clinical question is if there is solid organ injury to the liver, kidney, spleen, or pancreas. For the BEFAST exam the liver, kidney, spleen, and pancreas should be examined using a low mechanical index setting in contrast-specific imaging mode.

In order to determine interrater reliability of the ultrasound exams, the interpretation of the point-of-care EM physician (who will attest they are blind to the CT read and the ATLS FAST read) will be compared to the interpretations of two board-certified radiologists (blinded to the FAST reads and the CT read) for the presence or absence of solid organ injury, free fluid, or active extravasation. Injured organs will be graded per AAST criteria.

7. Video clips collected for this study will be saved for future education and training purposes, and also used in research presentations at national conferences.

8. N/a: The study does not target a particular community.

9. Participant Selection:

Requested sample size: 267; expected refusal or withdrawal rate – conservatively we set at 90%.

Inclusion Criteria: Age 18 and older Clinical suspicion of intra-abdominal injury (IAI) Presentation within 24 hours of injury Planned CT of the abdomen/pelvis within 24 hours Ability of patient to provide informed consent

Exclusion Criteria: Co-existing penetrating abdominal injury Known hypersensitivity reaction to contrast agent Pregnant patients Prisoners No appropriate IV Line able to be inserted Hemodynamic instability at time of enrollment (sustained systolic blood pressure < 90 mm Hg or sustained HR >120 despite initial resuscitation)

Justification:

We did not include pediatric population because FAST sensitivities are different in adult and pediatric populations.

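### Positive FAST and BEFAST findings go to the treating team, and nothing keeps them from the CT reader or records which came first, so the reference standard may not be independent of the tests it judges

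*Combined protocol and SAP*

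**What the plan says.** Section 13 (Statistical Analysis, Objective 1) compares BEFAST with FAST "when performed by frontline providers using CT as gold-standard". The primary analysis is stated as: "Agreement with the CT results will be examined using a mixedeffects/multi-level logistic regression in order to account for clustered measurements". Section 11 (Incidental Findings) adds: "All study patients will also obtain confirmatory imaging with CT study".

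Masking is described in Section 6. The bedside emergency physician is the one "who will attest they are blind to the CT read and the ATLS FAST read", and an attestation records any "unintended disclosure of either the primary team's FAST exam or CT imaging read prior to bedside interpretation of the BEFAST study". The interpretations used for inter-rater reliability come from "two board-certified radiologists (blinded to the FAST reads and the CT read"; these radiologists re-read the ultrasound, not the CT.

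On timing, the inclusion criterion is "Planned CT of the abdomen/pelvis within 24 hours". It does not say what the 24 hours runs from, or whether the CT is done or read before or after the study ultrasound. Section 6 records start and stop times for FAST and BEFAST.

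On disclosure, Section 11 says: "The research team will relay any findings related to injury to solid organs and hemoperitoneum to the primary treatment team for further management". It gives no time point and does not mention the CT reader.

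**The concern.** Sensitivity and specificity against CT mean what they appear to mean only if the CT is read without knowledge of the test being judged. A CT reader who hears that ultrasound showed a splenic injury or free fluid may look harder there and call an equivocal lesion positive. Only positive findings are relayed, so any such influence pushes CT reads toward positive. An ultrasound false positive then becomes a true positive for the exam that raised it and, if the other exam was negative, a miss for that one.

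The plan guarantees as few as 20 CT-positive patients, so one or two changed reads are enough to move the primary contrast. CT-positive status also feeds the rule for ending enrolment. Because neither the relay time nor the CT report time is recorded, nobody could later show whether the contrast had been affected, or in which direction.

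**Working it through.** **Step 1: who is masked to what.**
- Bedside physician: masked to the CT and the ATLS FAST, with disclosure recorded (Section 6).
- Two radiologists re-reading the ultrasound: masked to the FAST reads and the CT (Section 6).
- Reader of the reference CT: not identified, and no masking stated (Sections 6, 9, 11 and 13).
- Times: FAST and BEFAST start and stop are recorded; relay and CT report are not.

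All the protection runs from CT to ultrasound. None runs the other way.

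**Step 2: what is relayed.** The Section 11 sentence covers both organ injury and hemoperitoneum, and the sentence after it refers to both exams. Section 6 makes free fluid the FAST question and organ injury the BEFAST question. Positives from either exam can therefore reach the treating team.

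**Step 3: size.** The plan gives no figure to reproduce on this point, so this is an illustration.

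Inputs from Section 13 (Sample Size Calculations): sensitivities 0.87 and 0.68, specificities 0.98 and 0.95, 187 patients, at least 20 CT-positive. Assumed: x_B BEFAST-only and x_F FAST-only false positives are called CT-positive. With D CT-positive patients before any read changes:

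difference = (0.87D − 0.68D + x_B − x_F) / (D + x_B + x_F)

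| Changed reads | D = 20 | D = 37 |
|---|---|---|
| none | 3.8/20 = 19.0 points | 7.03/37 = 19.0 |
| x_B = 1 | 4.8/21 = 22.9 | 8.03/38 = 21.1 |
| x_B = 2 | 5.8/22 = 26.4 | 9.03/39 = 23.2 |
| x_F = 1 | 2.8/21 = 13.3 | 6.03/38 = 15.9 |
| x_F = 2 | 1.8/22 = 8.2 | 5.03/39 = 12.9 |

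D = 37 is about 20% of 187. Section 4 puts the yield of abdominal CT in blunt trauma below 20%.

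**Step 4: how many false positives there are to change.** With 187 − 20 = 167 CT-negative patients, expect 167 × 0.02 = 3.34 BEFAST and 167 × 0.05 = 8.35 FAST false positives. Two changed reads would be about 60% of the former (2/3.34) or 24% of the latter (2/8.35).

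**Step 5: a common fraction f of false positives changed (f is assumed).**
- BEFAST false positives only, 5% of them also FAST-positive. At f = 0.25: (17.4 + 0.835)/20.835 − (13.6 + 0.042)/20.835 = 0.875 − 0.655 = 22.0 points. At f = 0.5: 24.9 points.
- Both exams' false positives, treated as not overlapping. At f = 0.25: (17.4 + 0.835)/22.92 − (13.6 + 2.0875)/22.92 = 0.796 − 0.684 = 11.1 points. At f = 0.5: 5.0 points.

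The direction depends on which exam's findings sway the reader.

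**The case against.** The strongest reply is that the path is inferred. The relay goes to the treating team, and nothing says it travels on to the CT reader. Bias needs the ultrasound and the relay to precede the CT read, onward transmission, and a lesion open to interpretation. The attestation about CT disclosure shows that the CT may already have been read in some patients. A more careful read might also recover a real injury, since Section 4 gives CT a sensitivity of 97-98%. All of this stands, and it limits how often the problem can arise. It does not remove it: the plan neither blocks the path nor records whether it was open. Even a better read breaks independence if the extra care is given only to ultrasound-positive patients.

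A reader might go further and infer that the relay favours BEFAST. BEFAST names organs and grades injury, so it might pull harder on the CT reader than FAST, which looks for fluid. That is a reason to suspect asymmetry, not evidence of it. FAST hemoperitoneum is relayed too, and equal influence would shrink the difference (Step 5). Nor do the documents support reading the criterion as a CT that follows BEFAST by up to 24 hours, because the order and the starting point are not stated.

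**Conclusion.** The gap is real and should be closed: the reference CT read is unprotected against knowledge of the index tests, and the plan collects nothing that would reveal contamination. It applies only to patients whose findings were relayed before the CT was read, and that share is unknown. With 20 CT-positive patients and one or two changed reads, the 19-point difference could lie anywhere from about 8 to about 26 points; with 37, from about 13 to about 23. These ranges rest on the plan's own sensitivities and on an assumed number of changed reads, with the other exam negative in each affected patient. They show how fragile the contrast is and are not an estimate of bias. No direction can be claimed.

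**What to change.** Leave the relay to the treating team unchanged.

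1. State that the research team does not give study FAST or BEFAST results to the CT reader and that, where care allows, those results are not put in the CT request. The second part is needed because the likely route is through the treating team.
2. Record the time of relay, the time of the final CT report, and whether the CT reader knew the results. Exam start and stop times are already collected.
3. Add a sensitivity analysis of the primary contrast by order: CT report final before relay versus after. For patients with nothing to relay, use the BEFAST stop time. In the CT-first group, keep only exams where the sonographer attested no CT disclosure, since that is where the sonographer's own masking is most at risk.
4. Do not simply drop relayed patients. Only positives are relayed, so dropping them would selectively remove ultrasound positives.

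The cost is a short protocol statement, three data fields and one analysis, with no extra reader. The downside is precision: with perhaps 20 CT-positive patients in all, each order group will be small, and the comparison can reveal only a large effect. A masked re-read of the CT would be more direct, but it needs an additional reader.
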